1. PROJECT REVIEW

New project: **Optimization of a new adaptive intervention to increase COVID-19 testing among people at high risk in an urban community**
 Resubmission project:
 Date of most recent previous review:

2. DATA COLLECTION DATES 01/04/2021 - 05/12/2022

3. INVESTIGATOR(S) (copy and paste additional investigator names as needed):

Investigator Name: [name]
Department: Research, NJCRI
Address: [name]
[contact] x 281
Email: [contact]

Investigator Name: [name]
Department: School of Social Work, University of Illinois at Urbana-Champaign
Address: [name]
[contact]
Email: [contact]

4. PROJECT TITLE/DESCRIPTION AND RECRUITMENT:

Title: Optimization of a new adaptive intervention to increase COVID-19 testing among people at high risk in an urban community

Little is known about the acceptability of COVID-19 testing in low-income and racial/ethnic minority neighborhoods, where residents experience increased barriers to prevention and treatment (e.g., unstable housing, higher risk jobs). In this study, community members and researchers will work together as partners with a community-based organization to test an intervention to increase COVID-19 testing and adherence to science-based COVID-19 treatment and prevention recommendations. We will adapt two cost-effective, evidence-based, and culturally appropriate interventions that have been successfully used to engage people in HIV testing and treatment. Navigation services (NS) increase HIV testing and adherence to treatment while addressing structural barriers that deter treatment engagement in high-risk communities. Brief counseling

increases HIV treatment engagement. The study will assess the impact of these interventions on COVID-19 testing rates and on adherence to science-based guidelines to prevention and treatment. The study will also produce in-depth qualitative data identifying ways to overcome barriers for those who do not accept testing or adhere to NJ COVID-19 recommendations.

This study is funded by the National Institutes of Health (NIH) as a supplement to our parent study optimizing *Community Wise*, an intervention to reduce substance use among formerly incarcerated men (R01 MD010629-01). The *Community Wise* optimization study is being conducted as community based participatory research (CBPR) with the Newark Community Collaborative Board (NCCB), a group of 20 community members, service providers, and researchers. NJCRI and the NCCB are the study's community partners, connected through the Principal Investigators. [name] is founder and chair of the NCCB; [name] is employed by NJCRI and is an original NCCB member. For this study, the NCCB will continue to use CBPR to optimize an adaptive intervention that will take people through the COVID-19 continuum of prevention, care and treatment, starting with outreach, followed by testing, prevention intervention for those testing negative, and recommendation to quarantine, treatment, and/or referral to community based services and/or contact tracing for those testing positive.

We will recruit an intent-to-treat sample of 670 adults and estimate 15% attrition for a final sample of 582. Participants in this clinical trial will be recruited through a combination of strategies. Fliers will be posted throughout Essex County in public spaces, restaurants, and health care clinics, and community based organizations. People who call the study will be encouraged to disseminate the study to their friends and family. The NCCB will reach out to their contacts and networks.

5. **PARTICIPANTS** (approximate number and all applicable categories):
Number of participants proposed: 670

 Female	 Inmates or prisoners
 Male	 Cognitive impaired persons
 Children (17 or younger)	 Non-English speaking persons
 Prisoners	
 Pregnant women	

6. **COST AND PAYMENTS: (Will there be incentives for this project?)**

Participants will receive \$30 for completing the baseline interview and \$40 for completing each of two follow-up interviews. A randomly selected sample of 35 participants who do not complete testing will receive \$50 for completing an in-depth, qualitative interview. Thus, an eligible participant could receive up to \$160 for completing all data collection activities.

7. **ATTACHMENTS:** All relevant project materials and documents, including

- Surveys, questionnaires, interview instruments
- Informed Consent and Assent (if applicable) forms
- Letters of approval on letterhead from cooperating agencies, schools, boards of education, etc.
- Debriefing statement or explanation sheet if applicable
- Participant recruitment materials (e.g., fliers, advertisements)
- Other:

8. **CONFIDENTIALITY OF DATA:** how data will be stored and collected

Data will be generated and collected through interpersonal computer assisted interviews, computer assisted self-interviews, group session audio recordings, in-depth qualitative interviews and SARS antigen tests for COVID-19. Each participant will complete an initial telephone screening, a computer-assisted baseline and two follow-up interviews (2 weeks and 5 weeks post

baseline) and at least one COVID test. The electronic files generated through data collection and the test results will be identified by code numbers only and kept in password-protected and HIPAA-compliant devices and cloud storage, separate from identifying information and available only to project staff. This helps to ensure that no identifying information will be disclosed in the unlikely event that computerized data are stolen or otherwise seen by unauthorized persons. All identifying electronic data will be destroyed immediately after data collection is completed. Signed consent forms and audio recordings will be kept for 3 years after study completion. De-identified electronic data will be kept indefinitely. Study participants may ask at any time to have recordings of their interview destroyed by calling/e-mailing one of the Principal Investigators at the numbers provided in the informed consent forms.

9. RISKS AND BENEFITS: Describe Risks and Benefits

The main potential risks of this study include inadvertent violation of confidentiality and emotional distress on the part of participants. The procedures described above are intended to prevent violations of confidentiality. It is important to be aware that the prospect of testing positive for COVID-19 may be a cause of substantial fear and anxiety among participants. We anticipate that more than half of our participants will be African American or Hispanic and may lack trust in medical science and practice as a legacy of medical mistreatment. Many participants will have lost loved ones to COVID-19 and all of them will be medically or socially vulnerable to poor outcomes if they become infected themselves. They live with disproportionate risk caused by any of several factors, including but not limited to employment as essential workers, poverty, inadequate or unstable housing and underlying medical conditions.

It is also possible that participants who decline testing and attend Critical Dialogue sessions may be disturbed by sensitive questions raised during those sessions. Questions and discussions regarding stigma, racism, discrimination and structural inequality may cause anxiety, anger, suspicion, or other emotions. While we expect our sample to be predominantly African American, there will be some White and Latino participants as well and talking about racism in the group will elicit strong emotions. Differences among group members have the potential to harm or cause discomfort for a participant or to revive psychological dynamics that could threaten to renew old conflicts. We are using a trained facilitator who is from the community and has a great deal of experiential knowledge dealing with these sensitive topics and with this marginalized population. In the unlikely event a discussion escalates to the point that it may challenge the safety of the group, there is an emergency protocol in place where trained clinical staff and security can intervene and deflect potential violence or stabilize medical emergencies.

The potential benefits to participants in this study and other members of the community are significant and may be long lasting. Significant short-term benefits include detecting and treating cases of COVID-19 and preventing further transmission of the disease. While participants are enrolled in the study, referrals to resources to address social determinants of health (e.g., housing, food insecurity) may provide immediate tangible benefits. In addition, if participants express a need for mental health assistance at any time, the project team and the NCCB are well equipped to either provide service or make appropriate referrals. After engaging in the interventions, participants may experience increased feelings of empowerment and self-esteem, both of which have been associated with improved health outcomes. If the study succeeds in reducing medical mistrust and increasing health literacy, those benefits may be long-lasting. Both the short-term and long-term potential benefits of this study justify the potential risks involved in participation.

10. INFORMED CONSENT: Description of consents

Eligible individuals will provide written informed consent before participating in the study. During the informed consent process, the study outreach worker or research assistant will explain the study design in detail, including its purpose, the source of funding, why individuals are invited to participate, what they will be asked to do, how long the study will last and how many people are expected to take part in the study. They will explain the processes of SARS antigen testing and

randomization, the interventions being tested, potential sources of risk and discomfort and measures designed to minimize both. They will answer all participant questions and will ask participants to describe in their own words what they expect to do in the study before obtaining signatures. Participants who do not comprehend the study description will not be enrolled. Participants who would like some time to think before deciding will be able to take informed consent material home with them for review and consideration. All participants who provide written consent will receive a copy of the consent document which, in addition to the study description outlined above, includes names and contact information (phone numbers and email) for the Principal Investigators and for the appropriate ethics officials at NJCRI.

## **Statistical Analysis Plan**

Data analysis: Aim 1. We will estimate the (1) differences in the effects of first-stage interventions (NS vs brochure), (2) differences in the effects of second-stage interventions (BC vs NS among those who complete testing and referral vs CD among testing decliners), and (3) differences in the effects of selected adaptive interventions on acceptance of testing and adherence to NJ recommendations. For the differences between NS and brochure, cross-tabulations of the interventions with each outcome will be generated, and crude odds ratios comparing the two will be calculated. For the effects of second-stage and third-stage interventions, we will perform a similar analysis as that for the first-stage interventions but on corresponding subsets as indicated in the specific comparison groups. The estimation of effects of embedded adaptive interventions will use weighted and replicated estimation techniques. Under these procedures, the data set will be restructured wherein an individual's outcome will be replicated in the data set depending on the number of adaptive interventions consistent with this outcome. Since randomization at both stages is based on equal probabilities, weighting is not necessary. The restructuring of the data set as described allows the utilization of standard statistical software for parameter estimation and hypothesis testing. A generalized linear model using logistic regression will be performed where estimation of model parameters will be done using generalized estimating equations due to the presence of replicated subjects. We will then use tests of contrasts to compare selected adaptive interventions. The analysis of the adaptive interventions will be done using PROC GENMOD in SAS. To adjust for baseline characteristics and test for their moderating effects, we will incorporate these terms and their interactions with first-stage, second-stage, and adaptive interventions in their respective models. Only the baseline characteristics will be used for adjustment, as outcomes of the first-stage intervention are biased if incorporated into this model. Odds ratios, 95% CI, and Wald's test for the effect of interventions and covariates will be obtained from these results. Sex/gender and race/ ethnicity will be among these covariates that we will consider for adjustment and moderation analysis.

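### Critical Dialogue (CD) is delivered in groups, but the referral vs CD analysis makes no allowance for a shared group effect; if there is one, the interval is too narrow

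*SAP*

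**What the plan says.** SAP, Statistical Analysis Plan (Aim 1), names the second-stage comparison "referral vs CD among testing decliners". Its method is carried over from the first stage: "For the effects of second-stage and third-stage interventions, we will perform a similar analysis as that for the first-stage interventions", applied to the relevant subset. At the first stage, each outcome is cross-tabulated by intervention and "crude odds ratios comparing the two will be calculated". Logistic models add baseline covariates and give Wald tests and 95% intervals. The embedded adaptive interventions (regimes) are compared in a logistic model "where estimation of model parameters will be done using generalized estimating equations due to the presence of replicated subjects".

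The Aim 1 text does not spell out CD. Reading it as Critical Dialogue rests on Protocol section 9, which says that "participants who decline testing and attend Critical Dialogue sessions may be disturbed by sensitive questions raised during those sessions". The same section shows that these sessions are group discussions: "talking about racism in the group will elicit strong emotions". Protocol section 8 lists "group session audio recordings" among the data sources, and the SAP section on additional analyses plans to record and transcribe the sessions for qualitative work. On delivery, Protocol section 9 says: "We are using a trained facilitator who is from the community".

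Neither document mentions an intraclass correlation (ICC), a random group effect, a group-clustered standard error, or a CD group identifier attached to the outcome data. The SAP section on non-adherence and missing data, which sets out the intent-to-treat and imputation rules, does not mention group membership.

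**The concern.** People who sit through the same discussion share its facilitation, its other members and how it goes. If that moves their later testing or adherence up or down together, the CD arm holds less independent information than its head count suggests. A crude odds ratio takes its standard error from the head count alone. The interval for referral vs CD would then cover less than 95%, and the test of no average difference would reject too often.

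The GEE does not repair this. Its clusters are the duplicate records of one person, so two members of one CD group still count as independent. At stake is the stated certainty of a named Aim 1 comparison and of the regime contrasts that draw on it.

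**Working it through.** **Figures in the plan.** The documents give no effect size, outcome rate or sample size for referral vs CD, so there is no figure to reproduce. The check is how far the planned test departs from 5% under stated assumptions.

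**Inputs.** From the SAP: equal randomisation at both stages, 95% intervals, Wald tests, and analysis as randomised. Assumed, because the documents are silent: attenders per group *m*, ICC, share of the CD arm attending *a*, and equal outcome rates in the two arms.

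**Formulas when a shared group effect exists.** Only the CD arm is grouped.
- CD-arm design effect: DEFF = 1 + *a*(*m* − 1) × ICC
- True over planned standard error: R = √[(DEFF + 1)/2]
- Actual type I error of a nominal 5% test: 2[1 − Φ(1.96/R)]

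| *m*, ICC | *a* | DEFF | R | Type I error | Coverage |
|---|---|---|---|---|---|
| 6, 0.02 | 1 | 1.10 | 1.025 | 5.6% | 94.4% |
| 8, 0.05 | 1 | 1.35 | 1.084 | 7.1% | 92.9% |
| 10, 0.10 | 1 | 1.90 | 1.204 | 10.4% | 89.6% |
| 6, 0.02 | 0.5 | 1.05 | 1.012 | 5.3% | 94.7% |
| 8, 0.05 | 0.5 | 1.175 | 1.043 | 6.0% | 94.0% |
| 10, 0.10 | 0.5 | 1.45 | 1.107 | 7.7% | 92.3% |

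Worked line: for *m* = 10, ICC = 0.10, *a* = 1, DEFF = 1 + 9 × 0.10 = 1.90; R = √1.45 = 1.204; 1.96/1.204 = 1.628; 2[1 − Φ(1.628)] ≈ 10.4%.

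**Simulation.** 20,000 runs per setting, with about 146 per arm (582 × an assumed 50% decliners ÷ 2 = 145.5) and outcome probability 0.5. With a shared effect, the planned test rejected in 5.5%, 7.1% and 10.8% of runs (all attend) and 5.4%, 6.1% and 8.3% (half attend), in the order of the table.

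**When the planned test is right.** Suppose correlation arises only because people of similar risk are placed together after individual randomisation. The CD arm as a whole is still a random draw of independent people, and grouping them adds nothing to the variance of the arm total. With people sorted by risk into groups at the same ICCs, the planned test rejected in 4.9%, 5.2% and 4.8% of runs (all attend) and 5.0%, 5.1% and 5.1% (half attend). The same reasoning covers the case where CD changes nobody's outcome.

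**What it does to an interval.** With assumed rates of 30% and 45%, 116 per arm, 10 per group, ICC 0.10 and full attendance, the odds ratio is 1.91. The planned interval is 1.11 to 3.28; allowing for groups, it is 1.00 to 3.63.

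**Regime contrasts.** The outcomes of CD participants enter every regime that includes CD, so the same component is missing there. How much it matters depends on whether CD groups mix the two first-stage arms. If they do, it is diluted, and between two regimes that both include CD it can largely cancel. If groups are formed within arms, two regimes with the same first stage are affected about as much as referral vs CD. The documents do not say how groups are formed. I give no figures here because they would need further assumptions about participants who complete testing.

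**The case against.** The strongest reply is that the documents contain no evidence of a shared effect. That stands. A reader might infer from the SAP section on interim analyses, which plans weekly review of fidelity ratings and of deviance, that delivery is expected to differ between CD groups. That text is general quality control over all facilitators; it does not name CD or predict variation between groups. Protocol section 9 describes one trained facilitator, which, if one person runs every group, removes one source of between-group variation. It leaves variation from the members and the discussion.

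A reader might also infer that group membership goes unrecorded. Session recordings are planned, so that is too strong. What is absent is a link from group to outcome.

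The third reply concerns cost, and it also stands. If correlation is only compositional, a group-based analysis is conservative. At 10 per group, ICC 0.10 and full attendance, simulated type I error falls to 1.4%, and 80% power falls to Φ(2.802 − 1.204 × 2.04) = Φ(0.346) ≈ 64% (2.04 is the t value on 31 degrees of freedom). The outcome data cannot by themselves separate the two sources. This argues against replacing the planned analysis, not against reporting a second one.

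Finally, nothing shows that groups are fixed. With open attendance, assigning a person to one group is only an approximation.

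**Conclusion.** The omission is clear from the text: CD is given in groups, and no planned analysis allows for them. Its consequence is conditional. With a shared group effect, the interval for referral vs CD is too narrow, by a factor of about 1.01 to 1.20 in standard error across the assumed settings. Without one, the plan is correct as written. The top of the range needs groups of 10, ICC 0.10 and full attendance together; at 6 per group and ICC 0.02 the effect is negligible.

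The stronger conclusion, that the planned analysis is invalid and must be replaced, is not supported: the documents neither show a shared effect nor give the quantities that would size it. The point is worth acting on because the remedy is cheap and the sponsor cannot tell which case applies without the group identifier.

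**What to change.** 1. Record a CD group identifier under the participant's code number and link it to the outcome data. Record how groups are formed: by schedule or enrolment order, and whether they mix first-stage arms. Do this before identifying data are destroyed (Protocol section 8). Fix a coding rule for anyone who attends more than one group.
2. Keep everyone in the randomised arm. Prespecify, alongside the planned analysis, a partially nested analysis of referral vs CD: a group-robust variance, or a random group effect in the CD arm only. Referral participants and CD non-attenders are clusters of one. Use a standard small-sample correction based on the number of actual CD groups, not on a count that includes the clusters of one.
3. In the regime GEE, cluster on CD group for attenders, with their replicated rows nested inside, and on participant for everyone else. Carry the clustering through the covariate-adjusted models and the imputed data sets.
4. If the two analyses differ, state the referral vs CD conclusion with that uncertainty.

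The cost is one linked variable, a coding rule and a second set of models. The standard error is about 1% to 20% larger in the assumed settings, and with a t reference the interval is about 2% to 25% wider; both are unnecessary if the correlation is only compositional. Error may stay slightly above nominal with few or unequal groups. With unequal groups of about 10, ICC 0.10 and full attendance, two simulations of one group-based correction gave 6.3% (146 per arm) and 6.8%. With 73 per arm it gave 7.8%, against 14.7% for the planned test. Shared-provider effects in other arms are not addressed, and an effect of a single CD facilitator could not be separated from the effect of CD.

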## **Methods for additional analyses (e.g., subgroup analyses)**

Aim 2: To identify other predictors of these outcomes, we will include these variables as covariates using logistic regression analysis. We will model probabilities of testing behavior (completed vs testing decliners) and adherence to NJ recommendations as functions of the first-stage intervention and other covariates in the logistic regression analysis.

**Qualitative component analysis:** Critical dialog sessions and in-depth interviews will be digitally audio-recorded and transcribed. Data will be entered into Atlas.ti, a qualitative data processing program. Analysis rooted in phenomenology and grounded theory will include continuous coding, comparison, and recoding to yield categories and connect experiences and themes. The analysis will focus on participant reports about their experiences with the intervention, barriers to testing and adherence to NJ recommendations, and suggestions on how to address these barriers.

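### For the testing outcome, BC vs NS among completers cannot be estimated, and the replicated GEE splits the known testers by an option that cannot affect whether they tested

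*SAP*

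**What the plan says.** In the SAP, Data analysis: Aim 1, two outcomes are named, acceptance of testing and adherence to NJ recommendations. For NS (navigation services) vs brochure, "cross-tabulations of the interventions with each outcome will be generated, and crude odds ratios comparing the two will be calculated". For later stages, "we will perform a similar analysis as that for the first-stage interventions but on corresponding subsets". The second-stage comparisons are "BC vs NS among those who complete testing and referral vs CD among testing decliners", which I read as brief counseling vs navigation for completers, and referral vs Critical Dialogue for decliners. No sentence limits any of these comparisons to one outcome.

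The SAP section on additional analyses shows how testing is coded: "We will model probabilities of testing behavior (completed vs testing decliners". That is the same split that forms the second-stage subsets.

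For embedded adaptive interventions, each person's "outcome will be replicated in the data set depending on the number of adaptive interventions consistent with this outcome". No weights are used, because both randomisations have equal probabilities. A logistic GEE then tests contrasts. The third part of Aim 1 concerns "differences in the effects of selected adaptive interventions on acceptance of testing and adherence to NJ recommendations", and the selected interventions are not listed.

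**The concern.** A person re-randomised to BC or NS has, by definition, already tested. If testing is counted once, nothing in the second stage can change that person's testing outcome. Two consequences follow.

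- The BC vs NS table for testing has an empty column, so its odds ratio does not exist.
- In the GEE, two adaptive interventions that share the first-stage option and the decliners' option have the same true testing rate, whichever option completers receive. The replication rule still treats them as different and gives each one only the completers who drew its option. The remaining completers in that arm are known to have tested, but they do not contribute to that rate.

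The first fault will be noticed as soon as the table is run. The second will not: the model fits, and it reports standard errors larger than the data require for one of the two named outcomes.

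**Working it through.** **Inputs.** From the SAP: the subsets, the outcome coding, the replication rule and equal allocation without weights. From the Protocol, recruitment section: 670 recruited, 15% attrition, 582 final. The 582 is recovered as 582 × 1.15 = 669.3, rounded up to 670, whereas 670 × 0.85 = 569.5. I use 570, or 285 per first-stage arm; the choice barely matters because n cancels from the ratios below. The documents give no testing rates and no power. Assumed: two options per branch, first-stage acceptance p = 0.3 to 0.7, later acceptance among decliners q = 0.2 to 0.3.

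**Step 1: BC vs NS among completers.** With, say, 150 completers per option, the cells are 150 tested and 0 not tested in each. The odds ratio is (150 × 0)/(150 × 0), undefined. A logistic fit to these data reported perfect separation, with standard errors of about 17,600 and 24,900.

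**Step 2: one adaptive intervention.** Take first-stage option a, decliner option c, and n people in the arm. The target is θ = p + (1 − p)q, which does not involve the completers' option.

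- Planned estimate under simple re-randomisation: the mean over the half of the arm consistent with the intervention, so V_plan = 2θ(1 − θ)/n.
- Estimate using all completers, p̂ + (1 − p̂)q̂: V_all = (1 − p)(1 − q)[p(1 − q) + 2q]/n.
- Ratio: V_plan/V_all = 1 + p(1 − q)/[p(1 − q) + 2q].

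The ratio rises with p and falls with q, so the extremes are at two corners:

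- p = 0.3, q = 0.3: 1 + 0.21/(0.21 + 0.60) = 1.26, a variance cut of 1 − 1/1.26 = 21%.
- p = 0.7, q = 0.2: 1 + 0.56/(0.56 + 0.40) = 1.58, a cut of 37%.

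Simulation at 285 per arm agrees (about 1.25-1.58, cuts of 20-37%). For p = 0.5 and q = 0.3 the standard errors are √(2 × 0.65 × 0.35/285) = 0.040 and √(0.5 × 0.7 × 0.95/285) = 0.034.

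**Step 3: CD vs referral within a first-stage arm, same completers' option.** Write q1, q2 and θ1, θ2 for the two decliner options.

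- Planned: (2/n)[θ1(1 − θ1) + θ2(1 − θ2) − 2p(1 − θ1)(1 − θ2)].
- All completers: ((1 − p)/n){2[q1(1 − q1) + q2(1 − q2)] + p(q1 − q2)²}.

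At p = 0.3, q1 = 0.3, q2 = 0.2, n times these variances is 0.663 and 0.520, a cut of 22%. At p = 0.7 with both q = 0.2 they are 0.568 and 0.192, a cut of 66%. Simulation gives about 21-66%. If both decliner rates are 0.3 and p = 0.3, the values are 0.711 and 0.588, a cut of 17%.

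**Step 4: balanced re-randomisation.** If exactly half of the T completers and half of the D decliners go to each option, the planned estimate is (T/2 + Y)/(T/2 + D/2), where Y is the number of later testers under option c. This equals p̂ + (1 − p̂)q̂, so the point estimates coincide apart from odd counts. The robust variance still estimates 2θ(1 − θ)/n, so it is too large by about the Step 2 ratio (25-57% in simulation).

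**Step 5: contrasts differing only in BC vs NS.** The true testing difference is exactly 0. The estimate is not: under simple re-randomisation at N = 582 its SD was 0.015 to 0.036 (here with q up to 0.5), reflecting only the chance split of completers.

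**The case against.** The strongest reply is that testing may not be a once-only outcome. The Protocol's confidentiality section allows for more than one COVID test per person and sets follow-ups at 2 and 5 weeks, and the completed/declined coding appears under Aim 2. A repeat-test outcome would make BC vs NS on testing meaningful. But neither document defines such an outcome or gives it a time point, and the Aim 1 subset is itself formed by completion of testing. This leaves a choice for the authors to record; it does not rescue the plan as written.

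A second reply is that the planned method is unbiased under equal allocation and that completers are replicated, not thrown away. Both are true. The loss is one of efficiency, or of conservative standard errors under balance. The SAP states equal probabilities and does not say whether allocation is simple or balanced.

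Three stronger readings go beyond the documents:

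- A reader might infer that the plan estimates eight interventions and tests every pair. Two options per branch would give 8 interventions with 4 distinct testing rates, and 4 of the 28 pairs would have a true difference of zero. But the SAP gives no count, limits contrasts to selected interventions, and refers both to third-stage interventions and to two stages, so the layout is inferred.
- A reader might infer a false-positive problem. The chance that at least one of the four null contrasts is significant is about 9-10% only if all four are tested under simple re-randomisation; under balanced allocation it was 0.0% in simulation.
- A reader might infer that precision is lost throughout. It is not: crude NS vs brochure, referral vs CD among decliners, and every adherence analysis are untouched.

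**Conclusion.** The point holds in two parts. First, with testing coded as completed or declined, the planned odds ratio for BC vs NS among completers cannot be estimated, and the SAP does not exclude it. This part needs no assumption beyond a once-only outcome.

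Second, for adaptive interventions on testing, the planned variance per intervention is about 1.25-1.58 times what the same data allow. Whether that is truly lost precision or an overstated standard error depends on the re-randomisation method, which is not stated. As an illustration under simple re-randomisation with N = 582, p = 0.6 vs 0.5 and q = 0.3, power for the first-stage contrast between interventions is 25% as planned and 33% using all completers. These sizes rest on the assumed rates and the two-options-per-branch layout.

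Any selected contrast that differs only in BC vs NS would have a true testing difference of zero. Whether any such contrast is selected is not stated.

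**What to change.** - Analyse BC vs NS among completers on adherence only.
- For testing, define adaptive interventions by first-stage option and decliner option. Estimate each rate as P(test | a) + P(decline | a) × P(later test | a, c), using all completers. Equivalently, replicate completers under both decliner options with weight 1 and weight decliners by the inverse of the observed allocation, D/D_c, where D_c of the D decliners received option c: (T + (D/D_c)Y)/(T + D) is the same quantity.
- Use delta-method or bootstrap standard errors. Do not use fixed weights of 1 and 2: in simulation under simple re-randomisation they recovered only 10-19% of the variance per intervention and almost nothing for CD vs referral, because they do not correct for the chance split of decliners.
- Keep the planned replicated analysis for adherence.
- List the selected interventions and contrasts separately for each outcome, and state how second-stage allocation is done.
- If a repeat test after stage two is the intended outcome, define it with its time point instead.

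Cost: SAP wording and analysis code. No new data or change to trial conduct.
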